### 3.3 SAFETY ENDPOINTS

Safety endpoints will include (1) major bleeding, as defined by the ISTR, and (2) clinically relevant, non-major bleeding, also as defined by the ISTR. Criteria for major bleeding, and CRNMB are provided below

1. Major bleeding
  - a. Fatal bleeding
  - b. Bleeding into a critical area or organ (e.g., intracranial, intraspinal, intraocular, pericardial, intra-articular, intramuscular with compartment syndrome, retroperitoneal)
  - c. Bleeding causing a fall in the hemoglobin level of 2 g/dL or more, or leading to transfusion of 2 or more units of whole blood or red cells
2. Clinically relevant, non-major bleeding
  - a. Bleeding requiring medical intervention by a healthcare professional

- b. Bleeding leading to hospitalization or an increase in the level of care
- c. Bleeding prompting a face-to-face (i.e., not just a telephone or electronic communication) evaluation

### 3.4 ADJUDICATION OF OUTCOME EVENTS

All patient-reported events will be investigated by the Clinical Coordinating Center, including obtaining information from healthcare facilities where the patient received treatment. An independent, central adjudication committee (ICAC) will review and adjudicate events in a blinded manner without knowledge of treatment allocation. During the study period, the ICAC will adjudicate all suspected occurrences of venous or arterial thromboembolic events, ischemic stroke, acute myocardial infarction, deaths, and re-hospitalization. The ICAC will also review all suspected episodes of bleeding and categorize adjudicated bleeding as major, clinically relevant non-major, or minor bleeding. The Committee will be provided with all relevant documentation related to the events. The criteria and definitions of the study outcomes, as well as the procedures followed by the Committee, will be described in an adjudication manual which will be provided to the ICAC members before the first meeting.

### 3.5 POWER AND SAMPLE SIZE

The primary analysis for this randomized trial will be an intention-to-treat comparison of a composite endpoint (CE) of venous thromboembolic events, including new, symptomatic proximal or distal deep vein thrombosis affecting the upper and/or lower extremities, pulmonary embolism, or thrombosis of other veins (e.g., cerebral sinus veins, splanchnic veins); arterial thromboembolic events, including new ischemic stroke, myocardial infarction, mesenteric or peripheral arterial thromboembolism; and all-cause mortality for up to 30 days after randomization across the intervention arms. This binary primary endpoint was used to power the study.

The MARINER trial reported a 2% event rate for a combined outcome of VTE, MI, CVA, or CV deaths in the placebo group (Spyropoulos, 2018). These rates are expected to be higher in COVID-19 patients who are discharged from the hospital. Recent information from patients discharged alive from the University of Pittsburgh Medical Center suggests that the 30-day mortality rate in this population could be as high as 4%. To be conservative, 4% was used as the expected CE rate of events for the no anticoagulant arm. An effect size of 35% percent risk reduction (risk ratio = 0.65) in the anticoagulant group compared to the no anticoagulant group was used to calculate the expected sample size for the study.

The analysis will use a group-sequential two-sample two-sided Z-test for proportions with pooled standard deviation to test the primary hypothesis at overall significance two-sided level alpha = 0.05. Four equally spaced interim analyses and one final analysis will use O'Brien-Fleming alpha spending boundaries for efficacy and the Hwang-Shih-DeCani boundaries for the futility reviews (O'Brien and Fleming, 1979; Hwang, Shih, and De Cani, 1990). In order to ensure an 80% power to detect a CE rate reduction of 35% through anticoagulation use, the study needs to enroll at least 2,530 participants per arm. Since the primary outcome is observed within 30 days of follow-up, the loss to follow-up and withdrawal of consent rates should be low, and it is estimated that CE will be missing on a maximum of 5% of the participants. Therefore, the sample size required for this study will be approximately 2,660 per

arm. The sample size has been calculated using 2,000 simulations in PASS 13 [PASS 13 Power Analysis and Sample Size bounds Software (2014). NCSS, LLC. Kaysville, Utah, USA, [ncss.com/software/pass](http://ncss.com/software/pass)].

The operating characteristics (type I error and power) of the design has been investigated through simulations under the bounds established in the interim analysis (Section 3.3 below) and under the above assumptions using multiple software packages. The Type I error and Power were both adequate.

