### 3.7.2 INTERIM ANALYSES FOR FUTILITY AND EFFICACY REVIEW

The trial design planned for 4 interim analyses and a final analysis at equally-spaced information points. At each interim analysis cumulative primary outcome data, and potentially the secondary analyses, will be presented to the DSMB. Based on the data, a decision to stop or continue the trial will be taken following the O'Brien-Fleming Rule. If the Z-statistic crosses the lower boundary, the trial will be stopped for futility while if the Z-statistic crosses the upper boundary, the trial will be stopped declaring anticoagulant to be effective in preventing CE. In either case, Stage 1 of the trial will end and secondary analyses, including subgroup analyses will be critical for driving adaptive changes made based on accrued data. Eligibility criteria, efficacy, and safety endpoints will be analyzed at predefined intervals to guide the design of subsequent stages to allow efficient use of data and resources to inform the adaptations in trial design.

Assessments of futility will be conducted at all interim looks, whereas efficacy will only be assessed starting at the third interim analysis (after 60% of the information accumulated; **Table 1**). For the efficacy and futility, O'Brien-Fleming analog alpha-spending function and Hwang-Shih-DeCani beta-spending function will be utilized to create the non-binding boundaries. **Table 1** and **Figure 2** provide specific efficacy and futility boundaries at each interim analysis.

**Table 1:** Stopping Boundaries for Efficacy and Futility based on Z-statistic above.

Look	Information fraction	Efficacy Boundary	Futility Boundary
1	20%	NA	0.1383
2	40%	NA	-0.5933
3	60%	-2.6686	-1.1439
4	80%	-2.2887	-1.5918
Final	100%	-2.0307	-2.0307

**Figure 2:** Stopping Boundaries for Efficacy and Futility based on the Z-statistic described above.

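### SAP 3.5 states 80% power for a design with futility stopping, but following the printed futility boundaries at every look gives about 68%

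*SAP*

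**What the plan says.** SAP 3.5 sizes the trial for four interim analyses and a final analysis, using O'Brien-Fleming "alpha spending boundaries for efficacy and the Hwang-Shih-DeCani boundaries for the futility reviews". The next sentence says that "to ensure an 80% power to detect a CE rate reduction of 35% through anticoagulation use, the study needs to enroll at least 2,530" in each arm. This is raised to about 2,660 per arm for up to 5% missing outcomes, and the calculation is attributed to 2,000 simulations in PASS 13.

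The section then refers to "simulations under the bounds established in the interim analysis (Section 3.3 below") and concludes: "The Type I error and Power were both adequate". It gives no figure for either quantity. The section it points to is headed "3.3 SAFETY ENDPOINTS"; the boundaries are in SAP 3.7.2.

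SAP 3.7.2, with the same table in Protocol 7.6.4, says: "Assessments of futility will be conducted at all interim looks". Efficacy is tested only from the third look. On the consequence of crossing it says: "If the Z-statistic crosses the lower boundary, the trial will be stopped for futility". Yet the same section says that a "Hwang-Shih-DeCani beta-spending function will be utilized to create the non-binding boundaries". Protocol 5.6.2 leaves the decision to stop with the DSMB.

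Protocol 7.2 gives the same sample size and power but names only the O'Brien-Fleming boundaries.

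**The concern.** A futility boundary that is obeyed ends some trials that would have gone on to succeed, so power falls unless the sample size allows for it. No such allowance is visible. The stated 2,530 per arm is slightly below the fixed-sample size for the same test with no interim looks (2,555, shown below).

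The printed boundaries are also demanding. With Z oriented so that positive favours apixaban, the trial stops at look 1 if Z is below -0.14, that is, if apixaban is only slightly behind. At look 3 it stops unless Z exceeds 1.14, and at look 4 unless Z exceeds 1.59.

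If 80% holds only when futility is ignored, SAP 3.5 overstates power for the stopping rule it describes. A reader of that section would take the chance of missing the planned effect to be 20% with the futility rule in force.

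**Working it through.** **Inputs.** From SAP 3.5: placebo rate 0.04; risk ratio 0.65, so apixaban rate 0.04 x 0.65 = 0.026; two-sided alpha 0.05; pooled Z-test; 2,530 evaluable per arm. From SAP 3.6: 1:1 allocation. From SAP 3.7.2: looks at 20, 40, 60, 80 and 100% of information, and these boundaries:

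| Look | Efficacy | Futility |
|---|---|---|
| 1 | none | 0.1383 |
| 2 | none | -0.5933 |
| 3 | -2.6686 | -1.1439 |
| 4 | -2.2887 | -1.5918 |
| Final | -2.0307 | -2.0307 |

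**Sign.** SAP 4.2 defines Z = (pP - pA)/SE, positive favouring apixaban, but the efficacy column is negative. The table works only if negative Z favours apixaban. It is read that way here, with all signs flipped so that positive is favourable.

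**Step 1: reproduce the stated figure.**
- Pooled rate (0.04 + 0.026)/2 = 0.033.
- Pooled SE at 2,530 per arm = sqrt(0.033 x 0.967 x 2/2530) = 0.00502.
- Drift = 0.014/0.00502 = 2.787.
- Fixed design, no looks: 2,555 per arm for 80%; power at 2,530 is 79.6%.
- Five looks, printed efficacy boundaries, futility never acted on: 78.9% by simulation, 78.6% by numerical integration.
- Monte Carlo SE of 2,000 simulations at 80% = sqrt(0.8 x 0.2/2000) = 0.9 points. The gap (80 - 78.9)/0.9 is about 1.2 SE.
- 2,530/0.95 = 2,663, in line with about 2,660.

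So the stated 80% is reproduced, within simulation error, when futility is ignored.

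**Step 2: apply the futility column.** Two methods were used: 1,000,000 simulated binomial trials with the pooled Z, and recursive numerical integration with drift 2.787.

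| Futility acted on at | Simulation | Integration |
|---|---|---|
| Looks 1-4 | 68.4% | 68.2% |
| Looks 2-4 | 70.7% | 70.3% |
| Looks 3-4 | 73.0% | 72.5% |
| Look 4 only | 75.6% | 75.2% |
| Never | 78.9% | 78.6% |

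The 68.4% lies (80 - 68.4)/0.9, about 13 SE, below 80%, so simulation error cannot explain it.

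Look 1 can be checked by hand. The mean of Z there is 2.787 x sqrt(0.2) = 1.247. The chance of falling below -0.1383 is Phi(-0.1383 - 1.247) = Phi(-1.385) = 8.3%, which matches the integration; the discrete binomial simulation gives 8.9%.

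**Step 3: where the type II error arises (futility followed at every look, simulation).** Cumulative futility stops under the planned effect are 8.9%, 15.8%, 22.0% and 27.2% at looks 1 to 4. Total type II error is 100 - 68.4 = 31.6%, so 31.6 - 27.2 = 4.4% reach the final look and fail there. Not all the 27.2 points are harm from the rule. The wins lost to it are 78.9 - 68.4 = 10.5 points; the other 27.2 - 10.5 = 16.7 points are trials that would have failed anyway.

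**Step 4: sensitivity.**
- 2,527 evaluable per arm (2,660 x 0.95): 68.3% followed, 78.9% never.
- All 2,660 evaluable: 70.6% followed, 75.2% at looks 3-4 only, 81.0% never.
- Type I error in the direction of benefit, 3.3% in both arms: 0.018 followed, 0.025 never.
- For scale only: with futility followed at every look, 80% power needs a drift of 3.218, hence about 2530 x (3.218/2.787)^2, or roughly 3,370 evaluable per arm; simulation at 3,370 gives 80.0%.

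**The case against.** The strongest reply is that the documents call the boundaries non-binding and leave stopping to the DSMB. On that reading the no-futility figure is the relevant one, and 79% is close enough to 80%. The second part stands: 79% is not an error. The first does not settle the matter. Non-binding means type I error is controlled even if a crossing is overridden; it says nothing about power when a crossing is obeyed. SAP 3.5 also names the futility boundaries as part of the design it sizes, and says power was checked under the boundaries.

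Other points carry some weight:
- The text says both that the trial will stop and that the boundaries are non-binding, so 68% is the full-compliance case. Discretion over futility gives something between 68% and 79%; stopping for safety or other reasons could lower power further and is not modelled.
- The 27 points of futility stops overstate the harm. The attributable loss is 10.5 points, and the fair comparator for the 32% miss rate is about 21% with no futility stopping.
- SAP 4.2 uses drop-outs' data up to drop-out, so the effective size may lie between 2,530 and 2,660. That moves the full-compliance figure only from 68% to 71%.
- Protocol 7.1 mentions a separate SAP for DSMB review, which is not available here, so what the DSMB was told is unknown.
- The figures depend on reversing the sign of Z defined in SAP 4.2. No other reading makes the table usable, but the conflict itself needs correcting.

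**Conclusion.** The concern holds. For 4.0% versus 2.6% and 2,530 evaluable per arm, the stated 80% is right, within simulation error, only if futility is never acted on (about 79%). With the printed column followed at every look, power is about 68%, and type II error under the planned effect is about 32%. Acting on futility only at looks 3 and 4 still gives only about 73%. With all 2,660 evaluable, the full-compliance figure is about 71%.

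This rests on the plan's rates, equally spaced looks, and the reading that negative Z favours apixaban in the boundary table. Type I error is not inflated and the final test remains valid. The fault is a headline power figure, and an unquantified assurance of adequacy, that do not describe the stopping rule printed in the same plan. The wrong section reference alone would be clerical.

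**What to change.** 1. **SAP 3.5, and Protocol 7.2 for consistency.** State power both ways, with the sponsor confirming the figures from its own simulations. For example: *With 4.0% versus 2.6% and 2,530 evaluable per arm, power is [about 68%] if the futility boundaries are followed at every look and [about 79%] if they are not acted on.*
2. **SAP 3.5.** Replace the statement that type I error and power were adequate with the simulated values of each, with and without futility stopping. Point to Section 3.7.2 instead of 3.3.
3. **SAP 3.7.2 and Protocol 7.6.4.** Reconcile the instruction to stop with the non-binding label. Tell the DSMB that following the column at every look gives a type II error of about 32% under the planned effect, against about 21% with no futility stopping. In the same edit, make the sign of Z in the table, the boundary text and SAP 4.2 agree.

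The cost is wording and a less favourable stated power. No patient, boundary, test or estimate changes. SAP 1.0 lets only the blinded statisticians modify the SAP after the first unblinded review; these edits need no unblinded data. Rebuilding the futility column or enlarging the trial is a separate trade-off for the sponsor and is not proposed here.

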### 3.6 RANDOMIZATION SCHEME

Randomization will be performed for study participants as close to the time of hospital discharge as possible. Hospitalized patients may be screened and approached about the study up to 48 hours before hospital discharge, but final enrollment and randomization should occur as close to the time of discharge as possible. Participants will be randomized in a 1:1 ratio using an online randomization system to either Arm A (apixaban 2.5 mg twice daily), or Arm B (matching placebo). Randomization will be stratified by (1) concomitant use of a single antiplatelet agent (yes/no), and (2) a maximal score of 5 or greater vs. a score of less than 5 by the World Health Organization (WHO) Ordinal Index.

### 3.7 INTERIM ANALYSES AND DATA MONITORING

#### 3.7.1 INTERIM SAFETY ANALYSES

Safety monitoring will be continuous. In addition to examining the rate of ISTH major bleeding and the rate of ISTH clinically relevant non-major bleeding (CRNMB) in each of the treatment arms, monitoring will include unacceptable toxicity, defined as major bleeding, including hospitalization, and all-cause mortality. Prior studies have shown that the rate of major bleeding will be very low. The degree of evidence about differences in risk of unacceptable toxicity from accruing data will be addressed on a regular and pre-determined basis (e.g. every 3 months or more frequently per DSMB request) and will be shared with the DSMB. Unadjusted safety event rates for each assigned treatment group, and relative risks, and the absolute risk differences with 95% confidence intervals, will be calculated and presented to the DSMB for each of the specified safety outcomes.

Events will be adjudicated centrally by an adjudication committee. The following events will be adjudicated: Hospitalization or Emergency Room/Department visit documented on the related Pharmacist form, DVT, PE or major bleeding is checked as event type, and SAE has hospitalization or prolonged hospitalization as a reason for seriousness.

**Appendix 2** provides a list of tables that are presented to DSMB every month.

Full DSMB report every three months, in addition, will contain the listings of all safety events, including the date of onset, relatedness to treatment/unexpectedness, resolution, treatment adjustment, and other detailed narratives. **Appendix 3** provides a list of tables and figures provided to DSMB every 3 months.

Additionally, participants with safety events will be categorized in comparison to those without the safety events using a logistic regression to identify if the safety event was associated with any particular participant characteristics to identify high-risk groups.

If safety issues arise, the DSMB will use their clinical and statistical judgment to assess the potential risks relative to the potential benefits. The DSMB may also examine the safety and efficacy data in subgroups known to be high risk for bleeding such as those with older age and/or higher BMI. The DSMB will use all available information to make recommendations to the NHLBI. The DSMB can recommend that the Post-discharge COVID-19 trial should continue as proposed, that one treatment arm or more may be dropped, that the trial protocol should be modified, or that the trial should be terminated early for safety reasons. At any of the safety reviews, the DSMB can request a further statistical evaluation of the safety data to make a decision. Only the DSMB and those individuals invited to the DSMB closed session is permitted to examine outcomes by the assigned treatment group. The DSMB will evaluate the rates of the primary endpoint and the safety endpoints by assigned treatment groups overall and within pre-specified subgroups.

[figure not shown]

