Participants can record events within an electronic patient portal. Participants can call to report an event. In addition, the Research Communication Center (RCC) is responsible for performing periodic assessments with the participants for adverse events.

If the RCC notes an unplanned medical contact by the participant (physician visit, emergency room (ER), Urgent care or hospitalization), the RCC will escalate to a pharmacist. The pharmacist will complete the Pharmacist Escalation Form within the EDC. Medical records will be obtained for hospitalizations, ER visits or if the pharmacist is unsure of potential endpoint or safety event. The coordinating center medical coordinator coordinates retrieval and upload of source documents for appropriate capture of the event(s) within the EDC. The coordinating center medical coordinator will provide the Pharmacist Escalation Form and received source documents to the coordinating center Core Medical Monitor.

The Core Medical Monitor will review the source documents to determine the event and will complete the AE/SAE form in the EDC including seriousness and causality to study drug prior for notification to DCRI Safety Surveillance.

SAEs, whether related or not related to study drug, and pregnancies must be reported to DCRI Safety Surveillance.

The Core Medical Monitors should report any SAE occurring after these aforementioned time periods, which is believed to be related to study drug or protocol-specified procedure.

An SAE report should be completed for any event where doubt exists regarding its seriousness.

If the Core Medical Monitor believes that an SAE is not related to study drug, but is potentially related to the conditions of the study (such as withdrawal of previous therapy or a complication of a study procedure), the relationship should be specified in the narrative section of the AE/SAE Form in the EDC.

Upon receipt by DCRI Safety, DCRI Safety will report to BMS within 1 business day of becoming aware of the event that is determined to be an SAE. SAEs will be recorded on either CIOMS or MedWatch form. The BMS Protocol number will be included on the cover sheet with the SAE form transmission.

The Sponsor Investigator designee will reconcile the clinical database SAE cases (**case level only**) transmitted to BMS Global Pharmacovigilance ([contact]).

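### The adjudication trigger list in SAP 3.7.1 is narrower than the scope in SAP 3.4 and Protocol 4.2.4, so clinically relevant non-major bleeding seen only in an office or urgent care can go unadjudicated

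*SAP*

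**What the plan says.** SAP 3.7.1 (Interim Safety Analyses) says which events will be adjudicated and gives three routes. The first is a hospitalization or ER visit recorded on the Pharmacist form; the second is that "DVT, PE or major bleeding is checked as event type"; the third is that the "SAE has hospitalization or prolonged hospitalization as a reason for seriousness". CRNMB, minor bleeding, death, stroke, MI and other venous or arterial events are not named.

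SAP 3.4 (Adjudication of Outcome Events) is wider. It says "the ICAC will adjudicate all suspected occurrences of venous or arterial thromboembolic events, ischemic stroke, acute myocardial infarction, deaths, and re-hospitalization", and then "The ICAC will also review all suspected episodes of bleeding and categorize adjudicated bleeding as major, clinically relevant non-major, or minor bleeding".

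Protocol 4.2.4 and A2.1 agree with SAP 3.4 on thrombotic events and deaths, but limit bleeding to episodes that need medical attention.

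SAP 3.3 counts as CRNMB, among other things, "Bleeding prompting a face-to-face (i.e., not just a telephone or electronic communication) evaluation". No care setting is specified.

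SAP Appendix 2, part D, has adjudicated tables with rows for major bleeding, CRNMB, minor bleeding, stroke, MI and all-cause mortality.

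Protocol A3.7 (Event Reporting) escalates to a pharmacist any "unplanned medical contact by the participant (physician visit, emergency room (ER), Urgent care or hospitalization". Medical records are then obtained for hospitalizations and ER visits, and otherwise only where the pharmacist cannot tell whether the contact is an endpoint or safety event.

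**The concern.** Two sections of the same SAP give different rules for what reaches the adjudication committee, and neither refers to the other. SAP 3.7.1 is written in terms of form fields, so it is the one a data system would most naturally implement.

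What is at stake is mainly CRNMB, because the bleeding cost of a prophylactic anticoagulant is likely to appear there first. In Protocol Table 2, non-major events make up most of the clinically relevant bleeding on active drug: 1.42% against 0.28% major in the MARINER row, and 4.1% clinically relevant against 1.1% major in the MAGELLAN row. Protocol A3.3 also sends the trial to the DSMB for a risk-benefit review when major or clinically relevant non-major bleeding on anticoagulant exceeds control by more than 5%. It does not say whether suspected or adjudicated counts feed that rule. If adjudicated counts do, incomplete CRNMB capture weakens it.

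**Working it through.** The plan gives no figure to reproduce here. The check is a comparison of the texts, followed by an illustration of size.

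**1. Event types against the SAP 3.7.1 routes**

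| Event | In SAP 3.4 scope? | Meets a 3.7.1 route? |
|---|---|---|
| Bleed seen in hospital or ER | Yes | Yes, route 1 |
| Bleed ticked as major, any setting | Yes | Yes, route 2 |
| Bleed seen only in an office or urgent care, not ticked major (can be CRNMB) | Yes | No |
| Minor bleed, no hospital or ER | Yes | No |
| Death outside hospital/ER with DVT, PE or major bleeding ticked | Yes | Yes, route 2 |
| Death outside hospital/ER with none of these ticked | Yes | No |
| Stroke or MI reaching hospital or ER | Yes | Yes, route 1 |
| Stroke, MI or other venous/arterial event never reaching hospital or ER | Yes | No |

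The table reads the routes as alternatives, which is the generous reading. The SAP joins the last one with 'and'; if they had to be met together, the list would be narrower still.

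For deaths, Protocol A3.7 lists death as a seriousness criterion separate from hospitalization, so route 3 does not cover a death at home.

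**2. Can the adjudicated tables be filled?** The CRNMB and minor-bleeding rows in SAP Appendix 2 D need events that the 3.7.1 list does not send to the committee. They can be completed only under the SAP 3.4 scope.

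**3. Illustration of size.** Inputs: CRNMB 1.42% on anticoagulant and 0.85% on placebo (Protocol Table 2, MARINER row) and n = 2,660 per arm (Protocol 7.2). The capture share c is an assumption, taken as equal in both arms. The rates come from a 45-day rivaroxaban trial, not 30 days of apixaban, so they only set a scale.

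Adjudicated difference = c × (1.42 − 0.85) = c × 0.57 points. Expected counts = 2,660 × c × rate. Power is the normal approximation for a two-sided 5% test of two proportions, Φ[(d − 1.96·SE0)/SE1], where d is the difference in proportions, SE0 uses the pooled proportion and SE1 the separate ones.

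| c | Events, active vs placebo | Difference (points) | Relative risk | Power |
|---|---|---|---|---|
| 1.00 | 38 vs 23 | 0.57 | 1.67 | about 50% |
| 0.75 | 28 vs 17 | 0.43 | 1.67 | about 40% |
| 0.50 | 19 vs 11 | 0.29 | 1.67 | about 28% |
| 0.25 | 9 vs 6 | 0.14 | 1.67 | about 16% |

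The relative risk is (c × 1.42)/(c × 0.85) = 1.42/0.85 = 1.67 at every c. It is computed from the rates, not from the rounded counts.

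**The case against.** The strongest reply is that the 3.7.1 list is not said to be exclusive. It sits in the interim safety section and names form fields, while the committee's scope is set by SAP 3.4, Protocol 4.2.4 and Protocol A2.1, which defer procedure to an adjudication manual. This stands to the extent that the harm depends on the list driving case flow, which the documents do not settle. It does not remove the conflict, because nothing says that SAP 3.4 prevails.

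Second, CRNMB does not vanish from view. Office and urgent-care contacts are escalated to a pharmacist, the DSMB receives a suspected-bleeding table by arm (SAP Appendix 2 C), and the three-monthly report lists all safety events. That is correct: the gap is in adjudicated classification, not in detection.

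Three stronger readings are tempting, and the documents do not support them:

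- *Home deaths drop out of the primary endpoint.* All-cause mortality in Protocol A2.2 needs no cause, so the death counts without adjudication. The DSMB would also see it: Protocol 5.6.2 has it review all deaths, SAP Appendix 2 C has a suspected-outcome mortality row, and SAP Appendix 3 D lists SAEs.
- *Stroke and MI are materially undercounted.* They are unnamed in 3.7.1, but Protocol A2.2 requires head imaging for stroke, and troponin and ECG changes for MI. Nearly all would involve a hospital or ER visit.
- *The relative bleeding risk is biased.* Under equal capture in both arms it is unchanged, as the working shows.

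**Conclusion.** The contradiction is real and can be read directly from the text. Its main consequence is that bleeding evaluated only in an office or urgent care can qualify as CRNMB yet meet no 3.7.1 trigger. If the list is applied as written, the adjudicated CRNMB and minor-bleeding rows would be incomplete and the absolute bleeding difference understated.

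The size cannot be derived from the documents, because they do not give the share of CRNMB handled outside hospital and ER. The reductions shown in the working rest on an assumed share, on equal capture in both arms, and on borrowed rates.

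A secondary consequence is that an out-of-hospital death with no DVT, PE or major bleeding ticked would be missing from the adjudicated mortality row. It might also never be assessed as a fatal bleed, which is a major-bleeding criterion. The primary composite itself is not affected. For stroke and MI the gap is minor.

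This should be corrected, since it concerns one of the two safety endpoints and the change is small.

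**What to change.** Amend SAP 3.7.1 to say that SAP 3.4 governs, and make the triggers alternatives. Add as triggers every death, every suspected venous or arterial event (including stroke and MI), and every suspected bleed with any medical contact, including the physician and urgent-care visits that Protocol A3.7 already escalates.

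Then reconcile the bleeding scope. SAP 3.4 covers all suspected bleeding; Protocol 4.2.4 covers bleeding that needs medical attention. The medical-contact trigger fits the protocol's scope and is meant to capture CRNMB, but self-managed bleeds would not meet it. If the SAP 3.4 scope is kept, those bleeds need a trigger too. If the protocol scope is chosen, SAP 3.4 should be narrowed and the minor-bleeding row in Appendix 2 D labelled as covering medically attended bleeds only.

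Cost: SAP wording, a trigger edit in the data system, and more packets for the existing committee. Some extra record retrieval is unavoidable, because Protocol A3.7 now obtains records for office and urgent-care contacts only when the pharmacist is unsure.
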